Chronic protein and calorie dietary restriction (PCR; reduced food intake without malnutrition) is known for extending longevity in multiple species¹⁸. PCR is also an established approach to positively impact metabolic fitness and resistance to multiple forms of acute stress¹⁹⁻²¹. Despite these wide-ranging benefits, potential clinical applications have never been considered feasible in humans due to the practical difficulties associated with voluntary food restriction combined with the assumption that PCR benefits take a long time to accrue. Recent preclinical studies by the applicants reveal a rapid onset of PCR benefits against surgically induced traumatic inflammation, IR injury, and the fibroproliferative vascular response to injury in rodents^{14-17, 22, 23}. Mechanistically, rapid changes in adipose phenotype and associated adipokine profiles appear to underlie these benefits¹⁶; but the key mediator appears to be endogenous H₂S. This field thus stands poised to move to clinical utility, and vascular surgery offers an optimal risk/benefit ratio for translation of the PCR/H₂S hypothesis¹⁵.

For the current project we propose a randomized, controlled trial to evaluate patient compliance and biologic mechanisms of a short-term pre-operative PCR diet in comparison to a normal ad libitum diet for 4 days before elective vascular surgery involving an open major operation. Both Endpoints relate to the long-term primary scientific objective to test the hypothesis that ***brief upregulation of endogenous H₂S via pre-operative PCR in elective major surgery improves clinical outcomes in humans***. After a successful pilot study of the PCR diet conducted inpatient before carotid endarterectomy titled Short-Term Endogenous Hydrogen Sulfide Upregulation (PHRC Protocol No. 2016P002507), we now aim to expand the study to at home diet among a variety of vascular surgery procedures. The primary endpoints of the study are:

- 1) Feasibility, and in particular outpatient subject compliance with PCR (measured by direct dietary intake data and serum markers including plasma free amino acids, pre-albumin, and insulin-like growth factor in comparison to the ad libitum diet).

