
Due to the high quantity of carbohydrates in the PCR diet, hypoglycemia will not be a major concern for subjects. However, at baseline we will screen diabetic patients for glucose control by questionnaire and HgbA1c testing. Those with very poor glucose control (HgbA1c >12%) will be excluded. Patients over the age of 65 on hypoglycemic agents (ie sulfonylureas) will hold their hypoglycemic agent medication for the four-day PCR diet intervention. Patients who have a baseline HgbA1c value less than 7% will decrease their insulin by

20%. Patients who report daily episodes of hypoglycemia will be reviewed by our study staff endocrinologist for glycemic control. Recommendations will be made to insulin dependent patients to check their blood glucose four times a day before meals and fasting while on the PCR diet. Our study staff endocrinologist will be available for patient consult in the event of PCR related hypoglycemia to change patients' insulin regimen.

We anticipate that there will be no significant adverse effects of the H2S upregulation and PCR diet but do expect a 20% dietary compliance failure rate. However, there may be additional risks or discomforts that are not known now.

Adipose biopsies add approximately 30 seconds to 1 minute to total surgery time but pose no other known risks.

Intellectual property and data generated under this project will be administered in accordance with Harvard policies. Materials and data will be transferred between BWH and material transfer and use agreements are already in place for such transfers. Publication of data shall occur during the project, consistent with normal scientific practices. Research data which documents/supports/validates research findings will be made available after the main findings have been accepted for publication.

Inadvertent disclosure of private medical information is a risk for study patients. Data records will be maintained in the locked Vascular Surgery Clinical Research office. Electronic files will be maintained on the Partners network drive, or securely input into selected professional data management system REDCap with access limited to study staff only.

Benefits

Patients may or may not benefit medically from taking part in this study. Theoretically patients receiving the PCR diet may have less chance of complications after surgery, but this is unproven. We do not expect to observe any physiological benefit if patients are randomized to the non-dietary restricted arm.

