The focus of this Mechanistic Trial is to gain insights into practical future trial construction considerations such as patient compliance and physiologic impact. We anticipate that the supervised PCR will be completed by a majority (~80%) randomized to that arm and that H_2S and H_2S production capacity will rise on day two and be significantly elevated above baseline until re-feeding POD#1. We expect that markers of stress will change significantly less in the active treatment group compared to normal diet group. Using an α of 0.05 and β of 0.8, based on the differentials observed in rodent work and factoring in non-compliance, via intent-to-treat the study is powered to test these two primary scientific markers (H_2S and norepinephrine/IL-6). Furthermore, we believe that there will be no significant adverse effects of the H_2S upregulation and PCR diet but do expect a 20% dietary compliance failure rate. Based on our own pilot work, we anticipate that markers of inflammation will be elevated (compared to non-atherosclerotic patient's samples in hand) in the enrolled subjects and further amplified by the surgical stress. We anticipate that the blood and adipose phenotypic signatures will have high inflammation, but that the subjects compliant with PCR will have a reduced global inflammatory activation state, and trends toward less carotid plaque inflammation and fewer postoperative complications. Our key endpoint for upregulation of endogenous hydrogen sulfide will be the P3 cell sorting assay. Based on pilot data we anticipate a 4% increase in the PCR diet cohort compared to ad lib diet controls, with an expected standard deviation of 8%. Using a power of 80% and an alpha of 0.05, and 8% specimen loss rate we need a sample size of $n=80$ to reach statistically meaningful conclusions (un-paired T-test). Importantly for future trials, we anticipate that the unbiased discovery platform will generate novel mechanistic hypotheses founded on human data and tissues that will be ripe for future research and translation.

References

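### The P3 calculation shows no allowance for the expected 20% diet failure, and n=80 does not give the stated 80% power either way: about 54% for a 4-point difference, possibly as low as 38%

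*Combined protocol and SAP*

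**What the plan says.** All references are to the combined protocol and SAP.

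- **P3 effect (Statistical Considerations).** P3 is named as the key endpoint for hydrogen sulfide upregulation. The planning effect is attributed to the pilot: "we anticipate a 4% increase in the PCR diet cohort compared to ad lib diet controls, with an expected standard deviation of 8" (both figures in per cent).
- **P3 sample size (same section).** "Using a power of 80% and an alpha of 0.05, and 8% specimen loss rate we need a sample size of"; the total given is 80, for an unpaired t-test. Whether the test is one- or two-sided is not stated.
- **Expected adherence (same section, and Foreseeable Risk and Discomforts).** The investigators "do expect a 20% dietary compliance failure rate"; correspondingly, about 80% are expected to complete the restricted diet.
- **Analysis principle (Statistical Considerations).** A separate sentence says that the study is powered on an ITT basis for H2S and for norepinephrine/IL-6, with non-compliance taken into account. That sentence rests on rodent differences, not on the pilot P3 figures.
- **Allocation (Approach and Methods).** 3:2, with 48 patients on the restricted diet and 32 on the usual diet.
- **Source of the pilot (Project Goals/Specific Aims).** "After a successful pilot study of the PCR diet conducted inpatient before carotid endarterectomy", this trial moves the diet to the home and to a wider range of operations. The pilot's compliance rate and analysis population are not given.

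**The concern.** The only allowance listed in the P3 calculation is the 8% specimen loss. That covers patients with no usable sample. It does not cover patients who give a sample but did not follow the diet. In an ITT comparison such patients stay in the restricted-diet arm and can pull its mean towards control. If the 4 points describes patients who took the diet, the difference to expect between the randomised arms is smaller than the one used for planning.

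At stake is what the trial can say about its key mechanistic endpoint. A reader who takes the 80% at face value would give a non-significant P3 result more weight than it can bear, in a study whose stated focus is to inform the construction of future trials.

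**Working it through.** **Inputs.** From Statistical Considerations: difference 4, SD 8 (standardised difference 4/8 = 0.50), alpha 0.05, power 80%, loss 8%, unpaired t-test, N = 80, compliance failure 20%. From Approach and Methods: allocation 48/32. My assumption: two-sided test (one-sided is also shown).

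**1. Reproducing n=80, with no dilution.** With r patients on the restricted diet per control,

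n(control) = (1 + 1/r) × (1.96 + 0.842)² × SD² / difference².

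For r = 1.5: 1.667 × 7.85 × 64/16 = 52.3, so 53 controls and 80 on the restricted diet, 133 evaluable. Dividing by 0.92 gives 145 randomised. The alternatives are:

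| Test and allocation | Normal approximation: evaluable / randomised | t-test: evaluable / randomised |
|---|---|---|
| Two-sided, 3:2 | 133 / 145 | 135 / 147 |
| Two-sided, 1:1 | 126 / 137 | 128 / 140 |
| One-sided, 3:2 | 105 / 115 | 105 / 115 |
| One-sided, 1:1 | 100 / 109 | 102 / 111 |

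No variant gives 80.

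**2. Evaluable numbers at n=80.** 48 × 0.92 = 44.2 and 32 × 0.92 = 29.4, so about 44 and 29.

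**3. Range of the ITT difference.** If non-compliers keep a fraction f of the effect, the ITT difference is 4 × (0.8 + 0.2f):

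- f = 1, or 4 points is already the arm-level difference: 4.0
- f = 0.5: 3.6
- f = 0: 3.2

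**4. Power at 44/29.** The standard error is 8 × √(1/44 + 1/29) = 1.91. The noncentrality is 4/1.91 = 2.09 at 4.0 points and 3.2/1.91 = 1.67 at 3.2 points. The noncentral t with 71 degrees of freedom, two-sided, gives:

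| ITT difference | Power |
|---|---|
| 4.0 | 54% |
| 3.6 | 46% |
| 3.2 | 38% |

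One-sided, the ends of the range are 66% and 50%. Without any specimen loss (48/32, two-sided) they are 58% and 41%.

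**5. Splitting the shortfall.** 80 − 54 = 26 points arise with no dilution at all. 54 − 38 = 16 points is the most that dilution to 3.2 adds. The total is 42.

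**6. Detectable difference.** At 44/29, 80% power needs a standardised difference of 0.679, and 0.679 × 8 = 5.4 points.

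**7. Would correcting N alone be enough?** With 133 evaluable (80/53), power at 3.2 points is 61%. Power of 80% at 3.2 points needs 208 evaluable by the t-test, or 208/0.92 = 227 randomised. The population to which the 4 points belongs would therefore still matter after the arithmetic was repaired.

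**The case against.** The strongest reply is that 4 points is already an arm-level difference. The plan ties it to the diet cohort as compared with controls, and Approach and Methods uses the word cohort for the assigned groups. Where Statistical Considerations means compliers, it says so. On that reading, multiplying by 0.8 discounts the effect twice. This stands as a possible reading, and it is why 3.2 points can only be the lower end of a range.

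Three further points support it:

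- The pilot figure may already include non-compliers, since its compliance rate is not given.
- Compliance failure has no stated threshold, so partial adherence with partial effect is plausible.
- Patients who find the diet too hard may withdraw (Foreseeable Risk and Discomforts). Those without a later sample would reduce numbers rather than dilute the mean. This does not restore power: at 4 points, losing all 20% from the restricted-diet arm leaves about 51% (29.4 against 44.2 × 0.8 = 35.3).

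The plan also says that non-compliance was taken into account. That statement concerns rodent differences and does not show that the P3 inputs were adjusted. Equally, it leaves the matter unclear rather than proving an omission.

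A reader might infer that the ITT difference is 3.2 points and that the trial simply has 38% power because of non-compliance. The documents do not support this. The 3.2 requires a pilot effect measured in compliers and no effect at all in non-compliers, and neither is stated. Nor do the documents show that dilution would be the likelier explanation of a null P3 result, or that such a result would be read as absence of upregulation.

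**Conclusion.** The point holds in conditional form. The P3 calculation shows no allowance for the compliance failure that the plan itself forecasts, and the plan does not say whether the 4 points refers to compliers or to everyone assigned the diet. Whichever is meant, 80% power is not delivered between 3.2 and 4.0 points. The larger and certain part of the gap is that n=80 does not follow from the stated inputs. The dilution part lies between nothing and 16 percentage points, depending on facts about the pilot that are not given.

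The headline figures assume a two-sided test, SD 8 in both arms and 8% loss in each arm. A one-sided test would raise the power, but not to 80%.

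**What to change.** Keep n=80 and amend Statistical Considerations as follows.

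1. State whether the 4-point pilot difference refers to compliers or to all patients assigned the diet in the inpatient pilot, and how non-compliance entered the P3 calculation, if it did. State that the test is two-sided, if that is intended.
2. Replace the 80% power claim for P3 with:

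> With 80 randomised 3:2 and 8% specimen loss (44 and 29 evaluable), power is about 54% for a 4-point ITT difference and as low as 38% if 20% non-compliance dilutes it to 3.2 points. The ITT difference detectable with 80% power is about 5.4 points.

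3. Report the P3 ITT difference with a 95% confidence interval.

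A complier-effect estimate (the ITT difference divided by the between-arm difference in compliance) is optional. It should be labelled supplementary, because it brings assumptions of its own.

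The cost is wording, plus looking up how the pilot figure was obtained. The stated power becomes less favourable. Recruitment, arms and procedures do not change.

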- 2) Measurement of H₂S and standard biological markers of stress in blood collected at baseline, immediately before surgery, and after surgery including stress hormones, oxidative stress, and inflammation. We will also collect intra-operative biologic samples of discarded tissues and a gram of adipose tissue (peri-vascular, subcutaneous) to inform potential mechanistic links between PCR induced H₂S upregulation and any perturbations in peri-operative stress responses.

A secondary exploratory aim is to compare clinical outcomes and complications between groups. These endpoints will include surgical and medical complications such as cardiac, neurologic, infectious, vascular,

wound, and any other clinically significant events that occur within 30 days of surgery. We will also look broadly at one-year survival and major cardiovascular events, though it is acknowledged that the project lacks fiscal resources to fully power this mechanistic trial for clinical efficacy.

Research Strategy (Background, Significance, Preliminary Data, Approach and Methods)

New Approaches are Needed to Reduce the Morbidity and Mortality of Vascular Surgery Procedures Elective surgery presents an opportunity unique in medicine: the planned stressful event. The need for and submission to surgery represents a major disruption in most patients' family and professional lives (including morbidity and mortality). Surgical mortality rates vary up to 1000 fold^{24, 25}, with vascular surgery carrying one of the highest rates of perioperative events. Much effort has been expended in studying methods of assessing and modifying the risk of vascular surgery²⁶. Several factors continue to challenge care in these patients. First, the population undergoing vascular surgery is getting sicker (e.g. higher prevalence of octogenarians²⁷ and diabetics²⁸). Furthermore, appropriate medical therapy to reduce CV events, particularly β -adrenergic blocking agent administration, remains an issue of great contention²⁹. Thus, the aging population, rising incidence of the metabolic syndrome, increasing vascular surgery access, and the lack of agreed upon mitigating medical therapy creates an environment susceptible for increased CV events with associated morbidity and mortality, all at enormous economic cost.

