Short-Term PCR Attenuates Intimal Hyperplasia Restenosis is a recurrent problem from vascular patients and applicable to a range of procedures. While fortunately an infrequent event, restenosis after CEA can lead to strokes and repeat interventions for patients⁷⁶. In a validated mouse model of the primary driver of restenosis, intimal hyperplasia⁷⁷, we discovered that a short-term pre-operative PCR diet resulted in less intimal area (p=0.032) vs controls. Mice on a PCR diet also had significantly larger internal elastic lamina length (p=0.003), a remodeling measure. Finally, the PCR cohort serum exhibited significant decreases in certain classes of circulating lipids, including a collapse of multiple triglyceride species, suggesting a fundamental shift in metabolism toward beta oxidation. In addition, the lowered levels of circulating triglycerides may help reduce secondary insulin resistance and inflammation.

Approach and Methods

Eighty subjects undergoing carotid artery endarterectomy, aortic aneurysm repair (open, and endovascular if groin cut down planned), open lower extremity arterial procedures (bypasses, aneurysm repair, arterial and bypass graft reconstructions), major amputation of the lower extremity (below knee and above knee amputations), or open hemodialysis procedures either symptomatic or asymptomatic disease will be recruited and enrolled at BWH. Using a randomized (3:2), parallel design, patients will receive either the PCR diet (n=48; ScandiShake [any of 4 flavors] mixed with almond milk, calculated individually for a total daily volume to achieve 30% caloric restriction and 70% protein restriction, based on body weight and activity level), or continued routine *ad libitum* diet (n=32). The Mifflin St. Jeor equation will be used to calculate the total 24-hour energy needs based on gender, age, height, weight, and activity factor for the PCR diet. Daily physical activity will be assessed by questionnaire to determine the activity factor for accurate calorie restriction calculations. The general ratio recipe for the ScandiShake is 85 grams ScandiShake powder to 240 cc almond milk. Water

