Data Collection

Time	< 30 Days Pre-op (Baseline)	4 days Pre-Op	3 days Pre-Op	2 days Pre-Op	1 day Pre-Op	Day of Op (Pre-Op)	Recovery Area	Post- Op Day #1	Post- Op Day #30 (+/- 14 days)	Post- Op 1 Year
Patient Screening (estimated n=600)	Enrollment, Randomization, Education (n=80)	Control Continue Usual Dietary Pattern (2:5 randomization)						NPO except meds	Resume Usual Diet	Study Participation Terminates
		Dietary Restriction Protein-Calorie Restriction x 4 days (3:5 randomization)						NPO except meds		
MealLogger app Entry		X	X	X	X	X	X		→ Post Op Day 14	
Blood Draw						X	X			
CBC with diff, Chem 7, lipidomics, cortisol, epinephrine, norepinephrine, dopamine, hs CRP, IL-6, leptin, HMW adiponectin, resistin, IGF-1, P3, serum pregnancy test (as needed); pre-albumin (baseline and preop)		X								
Determinations										
Physical Activity Questionnaire	X									
24-Hour Food Recall	X									
Height, Weight	X					X	X		X	
eGFR	X					X	X			
Wound Evaluation								X		
Tissue Collection*						X				
Full Medical History	X								X	
Satisfaction Questionnaire									X	
Physical Exam	X								X	
Chart Review										X
	Preprocedure					Inpatient		Post Procedure		Registry

*discarded artery, vein, peri-vascular or subcutaneous fat, aneurysmal specimens, and amputated tissues

Dietary compliance will be measured by way of dietitian calculated intake (for data analysis will be the gold standard). The subjects will be asked to document their meals using either the MealLogger app or paper

record. The MealLogger app allows subjects to take a picture of their meals, either the ScandiShake or their routine ad libitum diet. Study dieticians will interpret dietary intake through photos and directly contact subjects using the app for clarification of intake, or through paper record if subjects are unable to use the MealLogger app. Compliance with the dietary intervention will also be evaluated through measuring expected changes in the levels of plasma amino acids using an LC-MSMS platform, and insulin-like growth factor-1 (IGF-1) by ELISA. Because free amino acids are not stored in the body, PCR results in a rapid decline of essential amino acids, including methionine and tryptophan, that are monitored easily in blood plasma^{79, 80}. Isolated protein restriction also results in reduced plasma IGF-1, even in the absence of overall PCR⁸¹.

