H_2S and H_2S production capacity (two distinct entities, see *Cell* paper¹¹) will be longitudinally measured, as will stress and safety markers in blood samples taken prior to dietary intervention (PCR or control), after the dietary intervention but before surgery, and sequentially after vascular surgery. Blood samples will also be collected and analyzed by [name] team at Northwestern to assess for changes related to PCR. Adipose tissue biopsies from fat depots (subcutaneous, perivascular) will be taken at the time of surgery and analyzed for the effects of diet on lipid composition and on inflammatory markers predictive of the response to surgical stress. Additionally, discarded specimens (discarded artery, vein, peri-vascular or subcutaneous fat, aneurysmal specimens, and amputated tissues) will be collected and stored for microscopic analysis. Enrolled patients and their clinical data will be entered into a study-specific database within REDCap.

Statistical Considerations

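### The sample-size inputs stated for the P3 assay give about 54% two-sided power at n=80 (48/32 with 8% loss), not the stated 80%

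*Combined protocol and SAP*

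**What the plan says.** Statistical Considerations names the endpoint: "Our key endpoint for upregulation of endogenous hydrogen sulfide will be the P3 cell sorting assay". It then gives the assumed effect and spread: "we anticipate a 4% increase in the PCR diet cohort compared to ad lib diet controls, with an expected standard deviation of 8"%. The sample size follows: "Using a power of 80% and an alpha of 0.05, and 8% specimen loss rate we need a sample size of $n=80", with an unpaired t-test given in brackets as the analysis.

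Approach and Methods makes 80 the trial total and sets the allocation: "Using a randomized (3:2), parallel design, patients will receive either the PCR diet (n=48"), with 32 patients on the usual diet. The schedule under Data Collection also shows 80 enrolled.

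Two things are left open. The test is not said to be one-sided or two-sided. The 4% and 8% are not said to be absolute percentage points or relative changes.

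The same section has an earlier, separate power statement for H₂S and norepinephrine/IL-6: "based on the differentials observed in rodent work and factoring in non-compliance, via intent-to-treat the study is powered". It shows no effect size, spread or sample size. The section also expects 20% of patients to fail the diet, but the P3 calculation mentions specimen loss only.

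**The concern.** A difference of 4 with a standard deviation of 8 is half a standard deviation. An unpaired t-test at the usual two-sided 5% level needs well over 100 evaluable patients to detect that with 80% power, so a total of 80 before losses looked too small.

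P3 is the named key endpoint for H₂S upregulation, and measurement of H₂S is part of the second primary endpoint. This is also the only calculation with inputs shown that arrives at n=80. If the trial has much less power than stated, a non-significant P3 result could be read as evidence against the mechanism when the design had a large chance of missing the effect it assumed. The plan says its purpose is to inform how later trials are built, so the error would carry forward.

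The plan's own caveat, that "it is acknowledged that the project lacks fiscal resources to fully power this mechanistic trial for clinical efficacy", concerns clinical efficacy. It does not qualify the P3 statement.

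**Working it through.** **Inputs.** From Statistical Considerations: difference 4, SD 8, alpha 0.05, power 80%, specimen loss 8%, unpaired t-test. From Approach and Methods: 48 and 32 randomized.

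Assumptions: the 4 and the 8 are on the same scale, so the standardised difference is d = 4/8 = 0.5; the test is two-sided unless stated otherwise. Only the ratio matters, so points or relative change makes no difference if both figures share a scale.

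**Attempt to reproduce n=80.** By the normal approximation at 3:2:

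- Control arm = (1.96 + 0.8416)² × (8/4)² × (1 + 1/1.5) = 7.849 × 4 × 1.667 = 52.3, so 53.
- PCR arm = 1.5 × 53 = 79.5, so 80.
- Total evaluable = 133. The exact t-test power at 80/53 is 80.0%.
- Allowing for 8% loss: 133/0.92 = 144.6, so 145 enrolled.

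Forcing an exact 3:2 split under the t-test gives 81/54 = 135 evaluable and 147 enrolled. With 1:1 allocation, 128 evaluable are needed, and 128/0.92 = 139.1, so 140. None of these is near 80.

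**Power at n=80.** The noncentrality is d × √(n₁n₂/(n₁+n₂)), and power comes from the noncentral t distribution on n₁+n₂−2 degrees of freedom.

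- 48/32, no loss: 0.5 × √(1536/80) = 2.191; critical value 1.991; power 58.1%.
- 8% loss: 48 × 0.92 = 44.16 and 32 × 0.92 = 29.44, about 44/29. Then 0.5 × √(1276/73) = 2.090; critical value 1.994; power 54.1% (54.5% without rounding the arms). A 100,000-run simulation at 44/29 gave 54.3%.

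**What 44/29 can detect.** 80% power needs d = 0.679. At SD 8 that is a difference of 0.679 × 8 = 5.43. At a difference of 4 it is an SD of 4/0.679 = 5.89.

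**Readings that might rescue the figure.**

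| Reading | Power |
|---|---|
| One-sided, 44/29 | 66.5% |
| One-sided, 1:1 (40/40), no loss | 71.6% |
| Two-sided, 44/29, most favourable rounding (4.49 and 7.5) | 69.5% |
| One-sided, 44/29, same rounding | 79.8% |
| One-sided, 48/32, same rounding, loss ignored | 83.0% |
| 80 per arm, 8% loss, two-sided | 85.4% |

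The last reading contradicts the protocol, which gives 80 as the total. The 83.0% needs an undeclared one-sided test, extreme rounding of both inputs, and disregard of the stated specimen loss.

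**Baseline adjustment.** Data Collection plans "blood samples taken prior to dietary intervention (PCR or control), after the dietary intervention but before surgery", so a baseline-adjusted analysis may be possible. If 8 is the SD of a single post-diet value, the residual SD is 8 × √(1−ρ²). At 44/29 with 70 degrees of freedom, ρ = 0.5 gives 66.3%, ρ = 0.6 gives 73.1% and ρ = 0.677 gives 80.0%. The plan names only an unpaired t-test and gives no correlation.

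**Non-compliance.** The documents do not say whether the 4 is averaged over everyone assigned to the diet or applies to compliers only. If it is the former, power stays at 54%. If it is the latter, with 20% of the PCR arm non-compliant at 44/29:

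- no effect in non-compliers: 0.8 × 4 = 3.2, power 37.8% (37.1% when the mixture is simulated);
- half the effect (an assumption, not in the plan): 0.8 × 4 + 0.2 × 2 = 3.6, power 45.9% (simulated 45.6%).

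**The case against.** The strongest reply is that the plan never says the test is two-sided, so 54% takes the less favourable value of an unstated input. One-sided, the chance of missing a true difference of 4 is about 34% rather than 46%. Adding the most favourable rounding brings one-sided power to 79.8%. This stands as a reason to state the sidedness. It does not support the 80%: the inputs as printed give 66% one-sided, and even the extreme corner stays just under 80% once the plan's own specimen loss is applied.

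The scale of the 4% and 8% is also unstated. If they were on different scales, power could not be computed from the document at all. Reading both on one scale is natural, but it is an assumption, and the plan should remove the doubt.

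On non-compliance, the plan words the 4% as a contrast between the diet cohort and controls, which reads most naturally as an arm-level effect. The lower figures are therefore conditional and are not part of the main finding. The claim that non-compliance was factored in belongs to the rodent-based statement; nothing in the P3 calculation shows such an allowance.

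Finally, this is a mechanistic trial whose first primary endpoint is feasibility, and this calculation does not affect that endpoint. That is true, but an explicit 80% claim for the key H₂S endpoint should still follow from its inputs.

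**Conclusion.** The concern holds. The P3 statement does not follow from its own inputs. At n=80, split 48/32 with 8% loss, a two-sided unpaired t-test at 0.05 has about 54% power for a difference of 4 with SD 8, so a true effect of that size would be missed about 46% of the time against the 20% implied by the plan. The result rests on a two-sided test and on the 4 and 8 sharing a scale. Changing to a one-sided test raises power to 66% and leaves the conclusion as it is. Either the difference, the SD, the power or n is misstated, or an analysis was assumed that the plan does not describe; the document does not show which. This should be corrected before the plan is relied on, because n=80 has no other justification that can be checked.

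**What to change.** First check the 4 and the 8 against the pilot data. If both are right, keep n=80 and replace the P3 statement with wording such as:

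> With 48 and 32 patients randomized and 8% specimen loss (about 44 and 29 evaluable), a two-sided unpaired t-test at alpha 0.05 has about 54% power for a difference of 4 percentage points in P3 (SD 8 percentage points), and 80% power for a difference of about 5.4 percentage points.

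Change the units if the 4 and 8 are relative figures. Add one sentence saying whether the 4 is an intent-to-treat or a compliers-only effect. If it is compliers-only, report the reduced power under a stated assumption about non-compliers (about 37% to 46% under the two cases worked above).

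If the check finds a misstated input, correct it and show the recalculation. If a baseline-adjusted analysis was intended, name it as the P3 analysis and give the assumed baseline correlation; about 0.68 is needed for 80% power at 44/29, if 8 is the SD of a single post-diet value.

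The cost is protocol wording and a less favourable power figure, with no change to conduct or enrolment. Only a choice to hold 80% power for a difference of 4 with the unadjusted test would need more patients: 145 − 80 = 65.
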